This is a Phase 2, Prospective, Randomized, Multicenter, Open-Label, Controlled Trial. Patients are randomized to treatment with Exenatide SR + SOC vs. SOC alone at 4 months or 12 months post transplant after kidney transplantation and followed until 24 months after kidney transplantation. Patients who discontinued medication for AEs will be contacted within 30 days to follow up on the resolution of symptoms.

Study participants with prediabetes at 4 months or 12 months after kidney transplantation will be randomized 2:1 to receive either Exenatide SR or diet and exercise only with no medication. We plan to enroll approximately 50% of subjects at 4 months post transplant and 50% of subjects at 12 months post transplant

Primary Endpoint is the incidence of diabetes at 24 months after kidney transplantation.

Patients will be followed for 2 years after transplantation (20 or 12 months after enrollment) for progression to all endpoints. Therefore, there will be three SOC biopsies—4, 12 and 24 months after transplantation. Hemoglobin A1C will be performed at the same time points. In addition 2hOGTT will be performed if clinically indicated per our SOC.

Study Sites: This is a multicenter study involving the three Mayo Clinic kidney transplant programs. This group has a common IRB and can contract centrally. Collectively, they perform approximately 600 kidney transplants per year. They have a history of multicenter research trials—they enrolled 480 patients along with a fourth center in a recent NIH-sponsored trial that required a 1 year kidney biopsy (NCT01782586 Validation of Gene Expression Markers of Renal Allograft Functional Decline (<https://clinicaltrials.gov/ct2/show/NCT01782586?term=[name]&rank=10>)). Thus, this consortium is large enough to ensure enrollment in the time frame suggested, yet small enough to ensure collaboration and uniformity needed for these studies.

The patient visits and follow-up including safety laboratories all fall within the SOC follow-up at all sites. These include the biopsies. All clinical standard of care labs and biopsies are followed by clinical operating protocols and are followed by clinical nursing and physician staff.

Study drug:

Exenatide SR

Background.

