(DMGS). 77% of patients with diabetic nephropathy on 10 year biopsy did not have diabetes pre-transplantation, and 46% were in patients without overt diabetes pre- or post-transplantation, but with characteristics of prediabetes including fasting hyperglycemia and obesity. Furthermore, kidney transplants with DMGS had greatly inferior graft survival (Figure 1). These data suggest that a paradigm shift is needed to improve the long-term graft survival for kidney transplants.

PTDM is a pervasive problem. In a review of UTHSA kidney transplant recipients, the incidence of PTDM was 43% among Hispanics and 33% in non-Hispanic whites. Patients with PTDM had a higher BMI (BMI=30.4 kg/m²) compared with patients without PTDM (BMI=27.7 kg/m²). Based on preliminary data from our collaborative analysis of the University of Michigan Transplant Center cohort, 15% of 345 kidney transplant recipients who did not have diabetes pre-transplant had developed PTDM based on an OGTT done at 6 months post-transplant, and another 24% were prediabetic based on 2-hour glucose values which met the criteria for IGT. Similarly, the Mayo experience (a predominantly Caucasian population) noted a 33% incidence of IFG at 1 year among kidney transplant recipients without diabetes pre-transplant.

Study endpoints

Primary Efficacy Endpoint:

Incidence of diabetes at 24 months after kidney transplantation.

Diabetes is defined based on ADA criteria for diagnosis of diabetes;

HbA1C>6.5%

or FPG>126 mg/dl (fasting is defined as no caloric intake for at least 8 hours)

or 2h plasma glucose >200 mg/dl during an OGTT

or random plasma glucose >200 mg/dl in patient with classic symptoms of hyperglycemia

Based on published data, we expect that 30% of untreated patients with prediabetes at 4 months will develop diabetes by 12 months after transplantation. See statistical assessment section.

Patients also will be followed up to 20 months after enrollment for progression to other endpoints

Secondary endpoints

- To evaluate the prevention of progression to diabetes by 24 months after transplantation
- To evaluate the safety and tolerability of Exenatide SR
- To compare hemoglobin A1c levels in patients treated with Exenatide SR + SOC vs. SOC alone at 24 months after kidney transplantation.
- To compare the incidence of mesangial expansion >20% in patients treated with Exenatide SR + SOC vs. SOC alone at 24 months after kidney transplantation.

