Safety will be assessed using incidence of all adverse events (AEs), serious adverse events (SAEs), treatment-emergent adverse events (TEAEs) and AEs leading to study withdrawal; review of laboratory data, including hematology, renal function, biochemistry and microbiology and malignancies; new concomitant medication usage; hospitalization rates; and vital signs. Adverse events will be classified for serious adverse events using standard regulatory criteria.

Statistical analysis plan.

Study design and analysis will be performed according to intention to treat principles. Time to development of PTDM will be compared utilizing Kaplan-Meier curves generated according to the product limit method utilizing log-rank tests to evaluate intergroup differences. Risk adjustment for baseline differences between groups will be assessed according to multivariate proportional hazards models. Data on patients who withdraw or are lost to follow-up will be censored at the time of last visit. Comparisons of repeated measures between groups including the secondary endpoints outlined above will be performed utilizing general linear mixed models with transformation of data to logarithm forms when appropriate. These comparisons will be made with inclusion of subjects who withdraw within the follow-up period. Sensitivity analysis excluding these patients will also be performed.

Needed sample size was calculated according to development of PTDM based on utilization of a 2-sided chi-squared test at a 5% significance level and 80% power. The incidence of PTDM reported after kidney transplant varies from 2-50% with best estimates indicating that approximately 30% of patients will develop PTDM.^{3,4,41,42} The SCALE trial comparing GLP-1 receptor agonists to placebo showed an 80% reduction in development of type 2 diabetes.²¹ Other clinical trials evaluating prevention of diabetes showed a 30% risk reduction with metformin and 55-72% reduction with TZDs.^{29,43} Thus, sample size was calculated based on a proportion of 30% incidence of PTDM in the control group and 80% risk reduction in the experimental group (consistent with SCALE trial). A total of 81 (54:27 according to 2:1 randomization) patients will be required to achieve the power and significance levels above. In our preliminary data, 24-33% of kidney transplant recipients meet prediabetes criteria. We would expect that full enrollment would take 24 months.

Data management plan

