The coordinating center will be the primary contact for this study and the data coordinating center: [name] and his program coordinator, M [REDACTED] L [REDACTED] ([REDACTED] and [contact])

1. The FDA investigator-initiated IND will be held by [name]
2. Contracts will preferentially be through the Coordinating Center with subcontracts to the other sites. Indirect costs will be charged only once (i.e. at the site where the funds are actually spent).
3. Protocols will be approved by local IRB (the three Mayo sites have a central IRB).
4. Data is entered into a common database with case-report forms similar to any FDA studies(MEDIDATA Rave case forms specific for transplant are already in place)
5. The Coordinating Center will be responsible for data cleanup, data reporting and reporting to the sponsors and the FDA.
6. Histology:
Mesangial expansion by light microscopy

Schedule of visits

Enrollment Day 122 (4 months)

	Enrollment Day 122 after KTx range 90-180 days	Day 7±3 Days Post enrollment	Monthly labs to 1 year per SOC	Day 90±7	Day 365 ±90 after KTx	Labs q3 months from 12-24 months	Day 730 ± 90 after KTx
Consent	x						
Labs	x	x	x		x	x	x
Clinic visit	x				x		x
Communication through phone call or EMR		x		x		x	
HgbA1c					x	x	x
Biopsy	x				x		x
Pregnancy test	x						

Enrollment Day 365 (1 year)

	Enrollment Day 365 after KTx range 300-420 days	Day 7±3 Days Post enrollment	Labs q 3 months per SOC	Day 90±7	Day 730 ± 90 after KTx
Consent	x				
Labs	x	x	x		x
Clinic visit	x				x
Communication through phone call or EMR		x		x	
HgbA1c					x
Biopsy	x				x
Pregnancy test	x				

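### Entry cohort (4 or 12 months after transplant) is not stated as a stratum for the randomisation or the PTDM comparison, and the pooled Kaplan-Meier analysis has no stated time origin

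*Combined protocol and SAP*

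**What the plan says.** All points are in the combined protocol and SAP.

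- **Entry (Study design/schedule):** "We plan to enroll approximately 50% of subjects at 4 months post transplant and 50% of subjects at 12 months post transplant".
- **Follow-up (same section):** "Patients will be followed for 2 years after transplantation (20 or 12 months after enrollment) for progression to all endpoints".
- **Allocation (same section):** participants "will be randomized 2:1 to receive either Exenatide SR or diet and exercise only with no medication". No stratification factor is named, and no randomisation method is described anywhere.
- **Visit windows (Schedule of visits):** "Enrollment Day 122 after KTx range 90-180 days" for one cohort, "Enrollment Day 365 after KTx range 300-420 days" for the other, and a final visit at "Day 730 ± 90 after KTx" for both.
- **Primary endpoint (Study endpoints):** incidence of diabetes 24 months after transplant. The only cohort-specific risk is for 4-month patients: "we expect that 30% of untreated patients with prediabetes at 4 months will develop diabetes by 12 months after transplantation". No risk is given for 12-month entrants.
- **Analysis (Statistical analysis plan):** "Time to development of PTDM will be compared utilizing Kaplan-Meier curves generated according to the product limit method", with log-rank tests. No strata and no time origin are given. A proportional hazards model is to adjust for baseline differences, with no covariates listed. The sample size uses one 30% control rate for everyone.

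**The concern.** Entry cohort is known before randomisation and fixes how long a patient is at risk. Unless the hazards happen to offset the difference in exposure, the cohorts will have different cumulative risks. With only 27 controls, an allocation that ignores entry cohort can leave the arms with visibly different mixes.

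The second issue is what the curve measures. The endpoint is fixed at 24 months after transplant. Timed from randomisation, that point is month 20 for one cohort and month 12 for the other. Month 12 on a pooled curve is then 16 months after transplant for half the patients and 24 months for the rest. Beyond month 12, at nominal visit times, only 4-month entrants remain at risk. No single point on such a curve is the stated endpoint.

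**Working it through.** **1. The plan's own figure.** Inputs are 30% in controls, 30% x 0.2 = 6% on drug, 2:1 allocation, 80% power and two-sided 5%. The pooled proportion is (0.30 + 2 x 0.06)/3 = 0.14.

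Controls = [1.960 x sqrt(1.5 x 0.14 x 0.86) + 0.842 x sqrt(0.30 x 0.70 + 0.06 x 0.94/2)]² / 0.24² = (0.833 + 0.411)² / 0.0576 = 26.9, so 27. With 54 on drug the total is 81, as stated. Expected events are 27 x 0.30 + 54 x 0.06 = 8.1 + 3.2 = 11.3.

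**2. Chance imbalance if allocation is unstratified.** Assume 41 four-month and 40 twelve-month entrants and fixed totals of 54:27. The number X of four-month entrants among controls is hypergeometric.

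- Var(X) = 27 x (41/81) x (40/81) x (54/80) = 4.56, so SD(X) = 2.13.
- The arm difference in the four-month share is X/27 - (41 - X)/54, which equals X/18 plus a constant. Its SD is 2.13/18 = 11.9 points.
- The exact chance of a gap of 10 points or more is 0.35; 20 or more, 0.10; 25 or more, 0.035.

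**3. Effect of a 20-point gap.** Control risks by cohort (4-month/12-month) are assumed.

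- *No treatment effect:* shift = 0.20 x (difference between cohort risks).
- *Planned 80% reduction:* at 2:1, a 20-point gap puts the control share 13.3 points and the drug share 6.7 points from the overall mix. Shift = 0.133 x (difference in control risks) + 0.067 x (difference in drug risks), the latter being one fifth of the former. For 40/20: 0.133 x 20 + 0.067 x 4 = 2.9 points.

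| Control risks | Shift, no effect | Shift, 80% reduction |
|---|---|---|
| 35/25% | 2 points | 1.5 points |
| 40/20% | 4 points | 2.9 points |
| 45/15% | 6 points | 4.4 points |

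The planned difference is 30 - 6 = 24 points.

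**4. What a pooled control curve reads, timed from randomisation.** Assume equal cohorts, a constant hazard within each, no dropout, and 24-month risks pa (4-month entrants) and pb (12-month entrants) averaging 30%.

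- S(12) = 0.5 x (1 - pa)^0.6 + 0.5 x (1 - pb)
- S(20) = S(12) x (1 - pa)^0.4, because only 4-month entrants remain after month 12

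For 40/20: S(12) = 0.5 x 0.736 + 0.5 x 0.80 = 0.768, and S(20) = 0.768 x 0.815 = 0.626.

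| pa/pb | Curve at month 12 | Curve at month 20 | True average |
|---|---|---|---|
| 30/30% | 24.6% | 34.7% | 30% |
| 35/25% | 23.9% | 35.9% | 30% |
| 40/20% | 23.2% | 37.4% | 30% |
| 45/15% | 22.6% | 39.0% | 30% |

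If both cohorts share one constant monthly hazard and the average is 30%, the risks are 36.3% over 20 months and 23.7% over 12. The curve then gives each cohort's own figure at its own month, but still not the 30% average.

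**5. Visit windows.** Follow-up can run from 640 - 180 = 460 to 820 - 90 = 730 days for 4-month entrants, and from 640 - 420 = 220 to 820 - 300 = 520 days for 12-month entrants. Any part of the curve past day 520 comes from 4-month entrants alone.

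**6. Error rates.** These come from 2,000 simulated trials per scenario over the four risk pairs. Unstratified randomisation with an unstratified log-rank test has power 0.83, 0.83, 0.85 and 0.86; with both stratified, it is 0.82, 0.83, 0.85 and 0.85. Type I error is 0.036 to 0.064 across the versions tried, with a simulation SE of about 0.005.

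**The case against.** **The plan is silent on method.** A reader might infer that the trial randomises everyone from a single list. The text does not say so; it only fails to state stratification. The imbalance figures are therefore conditional on unstratified allocation.

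**The plan has a safeguard.** The proportional hazards model could include entry cohort, which is a baseline variable. This stands in part: no covariate is named, and the model changes neither the allocation nor what the curve shows.

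**Cohort risks are not documented.** A reader might infer that 12-month entrants are known to be at lower risk because they are diabetes-free at month 12. But 4-month entrants are equally diabetes-free at month 4. Unequal exposure is documented; the 40/20 split is an assumption.

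**The endpoint itself is sound.** A reader might infer that the primary endpoint cannot be interpreted. It can: diabetes status 24 months after transplant is a common time point and averages over the planned cohort mix. The criticism applies to the Kaplan-Meier analysis. That analysis is, however, the only PTDM comparison the plan specifies; the chi-squared test appears only in the sample size.

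**A transplant clock.** A reader might infer that the 30% expected by month 12 would appear as 0.5 x 30% = 15%, because 12-month entrants would sit in the denominator without being able to fail. That describes a transplant clock without delayed entry, and the plan names no clock. The supportable criticism is that the origin is unstated.

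**Conclusion.** The point holds as one of balance and interpretation. Two cohorts with different exposure are to be compared in a single analysis that names neither strata nor a time origin.

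Under unstratified allocation there is about a 10% chance of a cohort-share gap of 20 points or more. Such a gap shifts the risk difference by about 4 points (2 to 6) with no treatment effect, or about 3 points (1.5 to 4.4) under the planned reduction. Both ranges rest on assumed cohort risks and are modest beside the planned 24 points. Timed from randomisation, the pooled control curve misses a true 30% average by about 5 to 7 points low at month 12 and 5 to 9 points high at month 20, assuming constant hazards.

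A reader might infer that the test is biased or the trial underpowered. Neither follows. Imbalance under randomisation arises by chance, type I error stays near 5%, and power and the 81 patients are essentially unchanged.

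**What to change.** 1. Randomise 2:1 separately within each entry cohort, for example 14 controls of 41 and 13 of 40, which keeps 27 of 81. If enrolment has begun, stratify the analysis only.
2. State that time is measured from randomisation.
3. Stratify the log-rank test and the proportional hazards model by entry cohort.
4. Report incidence at 24 months after transplant by arm as a cohort-stratified difference, for example Mantel-Haenszel.
5. Show within-cohort incidence descriptively only. Each cohort has about 13 or 14 controls, so at 30% the standard error is sqrt(0.3 x 0.7/14) = 12 points.

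The cost is two randomisation lists and slightly more analysis work, with no added patients or visits. The gain is balance and an estimate that matches the stated endpoint, not power. Because the trial is open-label, the clock and strata should be fixed before outcome data are reviewed.

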- To compare the incidence of mesangial expansion >20% in patients treated with Exenatide SR + SOC vs. SOC alone at 24 months after kidney transplantation.
- To compare transplant kidney function in the two arms
- To compare the incidence of death by any cause in the two arms
- To compare the incidence of graft loss by any cause in the two arms.

Inclusion criteria:

- Recipients of solitary kidney transplants (i.e. not combined liver-kidney, pancreas-kidney etc.)
- Labs consistent with prediabetes, as determined at 4 and 12 months after transplantation: Prediabetes (fasting blood glucose 100-125 mg/dl; or 2 hr glucose 140-199 or HgbA1c 5.7-6.4%)

Exclusion criteria:

- Diabetes pre-transplantation
- Diabetes at 4 and 12 months
- <18 years of age
- eGFR <30 ml/min (estimated by MDRD equation from serum creatinine)
- Active acute cellular rejection including borderline (If treated and resolved, these patients can be included)
- BK nephropathy active
- History of pancreatitis, pre-existing moderate-to-severe gastroparesis, liver cirrhosis or family /personal history of multiple endocrine neoplasia 2 or medullary thyroid cancer
- Pregnant or breastfeeding women

Female Subject must be either:

- a. of non-child bearing potential
 - 1) Post-menopausal (defined as at least 1 year without any menses) prior to screening , or
 - 2) Documented surgically sterile or status post-hysterectomy
- b. Or if childbearing potential,
 - 1) Agree not to try and become pregnant during the study for at least 90 days after the final study drug administration.
 - 2) And have a negative serum or urine pregnancy test.
 - 3) And if heterosexually active, agree to consistently use two forms of highly effective birth control.

- Hypersensitivity to Exenatide

Criteria for Discontinuation of Medication:

- Decrease in renal function to eGFR to < 30 ml/min after study initiation
- Decrease in eGFR by 50% on the 2 consecutive measurements without otherwise identified cause which maybe correctable (like high immunosuppressive medication level, rejection, urinary tract infection, etc)
- Intolerable GI side effects despite the optimal therapy
- Thyroid tumor
- Pancreatitis
- Hypoglycemia

Study design/schedule

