- To compare transplant kidney function in the two arms
- To compare the incidence of death by any cause in the two arms
- To compare the incidence of graft loss by any cause in the two arms.

Subject Safety

The consent process will inform a volunteer about the study, indicate that participation is voluntary and he/she has the right to stop at any time. Risks will be enumerated in the informed consent form and described orally during the consent process.

The potential risks to study participants include side effects of Exenatide SR (table 1) and medication interactions.

Table * Adverse Reactions Reported in ≥5% of Exenatide Extended Release Treated Patients with Type 2 DM in Monotherapy Trial

Symptom	Percent
Nausea	11.3
Diarrhea	10.0
Infection-site nodule	10.5
Constipation	8.5
Headache	8.1
Dyspepsia	7.3

*From the package insert

It will also inform volunteers about the rare more severe complications including: pancreatitis, renal impairment, hypersensitivity, C cell thyroid tumors (the risk in humans is not determined), development of antibodies to the medication, hypoglycemia when use with other medications for diabetes (oral or insulin)

DRUG INTERACTIONS

- May impact absorption of orally administered medications.
- Warfarin: Postmarketing reports with exenatide of increased INR sometimes associated with bleeding. Monitor INR frequently until stable upon initiation of BYDUREON therapy

Patients will be monitored for any drug interactions with immunosuppression and other medications. Immunosuppression levels will be monitored as outlined below. Recipients on Warfarin will be asked to monitor their INR through the local Anticoagulation Clinics or PCP as per patient's preference frequently and per local protocols until INR levels are stable.

Stopping Rules.

In general, the study drug is well-tolerated and we expect the same in kidney transplant recipients.

Enrollment will be suspended for any of the following:

- 2 hospital admissions that are deemed related to study drug
- A patient death in the study arm. This will be investigated for possible causal relation to study drug.

In addition, the investigator also has the right to withdraw patients from the study for any of the following reasons:

- Concurrent illness
- Occurrence of an unacceptable adverse event (see Individual stopping criteria, above).
- Patient request
- Protocol violations
- Non-compliance
- Administrative reasons
- Failure to return for follow-up

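### As printed, the primary-endpoint cut-offs leave one value per test (FPG 126 mg/dl, 2 h glucose 200 mg/dl, HbA1c 6.5%) that is neither prediabetes nor an event; the effect is probably small and the repair is minor

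*Combined protocol and SAP*

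**What the plan says.** Inclusion criteria: "Prediabetes (fasting blood glucose 100-125 mg/dl; or 2 hr glucose 140-199 or HgbA1c 5.7-6.4" (the last figure is a percentage). The three tests are joined by *or*, so one is enough to qualify.

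Exclusion criteria: "Diabetes at 4 and 12 months". No numeric limits are attached.

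Study endpoints, Primary Efficacy Endpoint: "Diabetes is defined based on ADA criteria for diagnosis of diabetes". The list that follows gives HbA1c strictly above 6.5%, then "or FPG>126 mg/dl (fasting is defined as no caloric intake for at least 8 hours", then "or 2h plasma glucose >200 mg/dl during an OGTT". A fourth criterion is a random glucose strictly above 200 mg/dl with classic symptoms; it has no prediabetes counterpart and plays no part in this point.

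Statistical analysis plan: "Time to development of PTDM will be compared utilizing Kaplan-Meier curves generated according to the product limit method utilizing log-rank tests". The sample size rests on "a proportion of 30% incidence of PTDM in the control group and 80% risk reduction in the experimental group", with 81 patients split 54:27.

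No other section classifies 126, 200 or 6.5%. The primary objective refers only to the ADA diabetic range, and Specific Methods names the tests without limits.

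**The concern.** Upper limits of 125, 199 and 6.4% suggest that diabetes begins at the next reportable value. The printed endpoint skips that value on each of the three tests. Two things follow.

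- **Outcome.** A patient who moves from prediabetes to exactly 126, 200 or 6.5%, and meets no other criterion, is not counted as progressing. Only about 11 events are expected, so single classifications can carry weight.
- **Entry.** The diabetes exclusion has no numbers of its own. If the endpoint definition governs it, a patient can enter on one test while sitting on the boundary of another, and then becomes an event with a rise of one reporting step. A site that treats the boundary value as diabetes would exclude the same patient.

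**Working it through.** **1. The plan's sample size.** Inputs from the Statistical analysis plan: control 0.30; experimental 0.30 × (1 − 0.80) = 0.06; 2:1 allocation; two-sided 5% chi-squared test; 80% power. The pooled rate is (0.30 + 2 × 0.06)/3 = 0.14.

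n(control) = [1.96 √(1.5 × 0.14 × 0.86) + 0.842 √(0.30 × 0.70 + 0.06 × 0.94/2)]² / 0.24² = 26.85, rounded up to 27.

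That gives 27 + 54 = 81, as stated, with power 80.2%. The cut-offs do not enter the formula. Expected events: 27 × 0.30 + 54 × 0.06 = 8.1 + 3.24 = 11.3.

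**2. The ranges side by side.** Assumed reporting steps: 1 mg/dl and 0.1% (the documents do not state them).

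| Test | Prediabetes ends | Event rule as printed | First event value | Unclassified | Unclassified if at-or-above |
|---|---|---|---|---|---|
| FPG, mg/dl | 125 | >126 | 127 | 126 | none |
| 2 h glucose, mg/dl | 199 | >200 | 201 | 200 | none |
| HbA1c, % | 6.4 | >6.5 | 6.6 | 6.5 | none |

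As printed, events begin two reporting steps above the prediabetes limit. The gap is per test: because criteria are joined by *or*, another test can still make the patient an event, or still place the patient in prediabetes.

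**3. Entry.** Take FPG 110 mg/dl and HbA1c 6.5%. FPG meets inclusion. If the endpoint definition governs the exclusion, HbA1c 6.5% is not diabetes and the patient can be enrolled.

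**4. How sensitive the test is to single events.** With no censoring and all events recorded at month 24 (both assumed), the log-rank statistic equals Pearson's chi-squared × 80/81. For 7/27 standard care vs 4/54 exenatide: 81 × (7 × 50 − 4 × 20)² / (27 × 54 × 11 × 70) = 5.26; × 80/81 = 5.19; p = 0.023.

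| Events, standard care (of 27) vs exenatide (of 54) | p |
|---|---|
| 8 vs 3 (near the expected split) | 0.003 |
| 5 vs 3 (three standard-care events uncounted from 8 vs 3) | 0.067 |
| 7 vs 4 | 0.023 |
| 6 vs 4 (one standard-care event uncounted from 7 vs 4) | 0.058 |
| 6 vs 3 (one event uncounted in each arm from 7 vs 4) | 0.025 |

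From 8 vs 3, one or two uncounted standard-care events leave the result significant. Exactly 7 vs 4 has probability 2.9% at the planned rates. With distinct event times and no censoring, p for 6 vs 4 runs from 0.039 to 0.073 depending on their order.

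**5. Over all possible results.** Enumerate Bin(27, 0.30) × Bin(54, 0.06), using the single-time log-rank test and assuming the planned rates hold under the at-or-above definition. P(significant) = 82.4%.

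| Uncounted events | Significance lost | Significance gained |
|---|---|---|
| One in each arm | 1.9% | 0.2% |
| One, standard care only | 11.1% | not applicable |
| Two, standard care only | 24.6% | not applicable |
| One, exenatide only | not applicable | 6.6% |

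These figures show what an uncounted event would do. They do not show how likely a boundary value is.

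**The case against.** **The sign may have been lost when the PDF was read.** The prediabetes limits fit an at-or-above reading exactly, and an underlined sign can drop out. If so, the plan contains no error. Against this, the at-or-above sign survives in the adverse-reaction table, "Adverse Reactions Reported in ≥5% of Exenatide Extended Release Treated Patients", and in the safety outcome measures, and the at-or-below sign survives under Light Microscopy. The first of these comes from the package insert, so the evidence is not decisive. The source check has to come first.

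**The reference to ADA criteria settles the boundary.** It shows intent and may guide adjudication, but the operative text is the printed numbers. A reader might infer that the protocol departs from the ADA criteria. That cannot be confirmed from the documents and is not needed: the mismatch is between two of the protocol's own sections.

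**Few patients will be affected.** This largely stands. The OGTT is done only when clinically indicated, so 200 should seldom arise. Patients enrolled at 4 months have HbA1c every 3 months from month 12 to 24, so a reading of 6.5% may only delay an event.

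**The one-arm figures are selective.** This also stands. The rule applies to both arms, and losing only standard-care events is the less favourable case. A reader might infer from 7 vs 4 that one boundary patient would typically overturn the trial; near the expected split it would not.

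**Open-label conduct.** A reader might infer biased classification. Three of the four criteria are laboratory values alone, and nothing in the documents shows differential misclassification.

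**Conclusion.** The point holds as a minor inconsistency in the definition of the primary endpoint. If the signs are as printed, and at the assumed reporting steps, one value per test belongs to neither range, and nothing else in the plan classifies it. The entry consequence is conditional on the endpoint definition governing the diabetes exclusion, which the plan does not say.

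The impact is probably small: significance is lost in about 2% of trials with one uncounted event in each arm, and in about 11% with one in standard care alone, under the assumptions given. How many patients will sit on a boundary cannot be determined from the documents. It would go too far to say that the gap favours either arm, since the rule is common to both and uncounted events can move the result either way. It would also go too far to say that the sample size is wrong: 81 reproduces exactly, from planning rates that are not derived from the cut-offs.

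**What to change.** 1. Check the source file for a lost at-or-above sign in the primary-endpoint definition. If it is there, no change to the cut-offs is needed.
2. If the signs are as printed, reconcile the endpoint definition with the inclusion criteria so that events begin where the prediabetes ranges end: HbA1c ≥6.5%, FPG ≥126 mg/dl, 2 h glucose ≥200 mg/dl. State the reporting precision.
3. In either case, have the diabetes exclusion refer to the same definition, so that all three sites apply one rule at entry and at outcome.

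Cost: one source check, at most three signs, a line on precision and one cross-reference. No new data, visits or patients are needed, and the sample size stays at 81. The rule should be settled before outcomes are analysed.
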